5.9.4 Management of Overdose

Symptomatic and supportive treatment should be given in case of overdose (defined as more than 1 dose administrated within 24 hours).

If the dose of study drug exceeds the dose specified in the study protocol, and no relevant symptoms or signs occur, it is not necessary to record it in the case report form. However, the overdose itself must be recorded in the Overdose Report Form of Clinical Studies. For overdose accompanied by a serious adverse event, the SAE diagnosis/symptoms must be recorded in the Serious Adverse Event Form. If there is overdose with adverse event, and the adverse event is serious, this adverse event should be recorded in the Adverse Event Form. In addition, the overdose must also be recorded in the Overdose Report Form of Clinical Studies.

5.10 Concomitant therapy

Subjects cannot simultaneously receive other antitumor therapy at the entry in the study and throughout the study, including cytotoxic agent (except non-antitumor chemotherapy), radiotherapy, biological therapy, endocrine therapy, or any other study drugs, and traditional Chinese medicine with antitumor activity cannot be used either during the study. Systemic antitumor therapy or therapy with other study drugs must be ended 4 weeks prior to the enrollment in this study.

If it is necessary for subjects to receive radiotherapy for tumor during the study, the Fruquintinib therapy will be discontinued. If local radiotherapy is indicated for the subject (eg., local radiotherapy for relieving carcinous osteodynia), the investigator should sufficiently evaluate the possibility of tumor progression, the subject could resume the study drug 7 days after the end of local radiotherapy but the following conditions need to be met:

- Recovery from radiotherapy related and < NCI CTC-AE grade 2 toxicity;
- No progression of tumor.

5.11 Other concomitant treatments

Investigators need to follow the following guidelines and use concomitant medications carefully during the study, as to ensure the subject's safety to the maximum extent.

- The best supportive therapy is allowed during the study, but preventive use of antiemetic drug is not allowed. Other drugs that can trigger or exacerbate the clinical symptoms cannot be used concomitantly, and should be intensively monitored when their use is essential.
- It was demonstrated in the preclinical study that Fruquintinib was metabolized via hepatic cytochrome P450 3A4. The potent inducers of CYP3A4 enzyme, such as phenytoin, phenobarbital and rifampicin (not limiting to the aforementioned drugs) and the potent inhibitors of CYP3A4 enzyme, including ketoconazole, itraconazole, fluconazole, indinavir, erythromycin (not limiting to the aforementioned drugs) could significantly affect the metabolism of Fruquintinib in humans. Cautions should be exercised in enrollment of the subjects concomitantly given known CYP3A4 inducers and CYP3A4 inhibitors. If such drugs are administered concomitantly in the study, cautions need to be exercised in its use, and exposure and adverse reactions should be closely monitored.
- Subjects are allowed to take anticoagulant (e.g., warfarin), but relevant coagulation parameters, such as INR, need to be monitored; if it is required for treatment, low molecular heparin sodium can be used.
- The investigator decides the use of other concomitant medications, as to ensure the subject's benefit and safety.

All the drugs including the study drug must be recorded in the case report form.

5.12 Treatment compliance

The investigators should record the amount of the study drug dispensed and recovered with the date and the actual dose administered promptly and accurately for each subject, the actual dose administered should be in line with the dose required by the protocol. The compliance with the drug will be judged according to the drug counting dispensed, returned and lost in each cycle of treatment and at withdrawal from the study.

The drug inventory list should be inspected by the sponsor or its assigned monitors at any time. Patients are requested to return all the used or unused bottles of Fruquintinib to the study site, as to evaluate their compliance. At the end of study, all the materials provided, including partially used or empty drug bottle, must be returned to the study monitor.

6 Variables, evaluation plan and steps

Attached tables (Evaluation form)

Attached Table 1

Study Flowchart

Date Item	Screening	Treatment period									10 ² AEU	Follow-up period
		Cycle 1				Cycle 2		Cycle 3		Cycle 3+		
		-14 D 743D	Day 7	Day 14	Day 21	Day 28 (±1 day)	Day 42 (±2 days)	Day 56 (±2 days)	Day 70 (±3 days)	Day 84 (±3 days)		
Fruquintinib treatment ^b and PK collection	Group A	Xa(4mg, qd, daily)				Xa		Xa		Xa		
	Group B	Xb(5mg, qd 3-week on/1-week off)				X ^b		X ^b		X ^b		
Expansion part		X ^b								X ^b		
Signing Informed Consent	X											
Randomization	X											
Tumor assessment ¹	X						X			X		
Inclusion/exclusion criteria	X	X										
Previous disease/history of surgery	X											
Concomitant medication details	X	X	X	X	X	X	X	X	X	X	X	
ECOG score/ weight	X	X	X	X	X	X	X	X	X	X	X	
Vital signs ²	X	X	X	X	X	X	X	X	X	X	X	
Complete physical examination	X	X	X	X	X	X	X	X	X	X	X	

Date Item	Screening	Treatment period									1021ÆÚ	Follow-up period
		Cycle 1				Cycle 2		Cycle 3		Cycle 3+		
		-14 D 743D	Day 7	Day 14	Day 21	Day 28 (±1 day)	Day 42 (±2 days)	Day 56 (±2 days)	Day 70 (±3 days)	Day 84 (±3 days)		
Hematological examination ³	X	X	X	X	X	X	X	X	X	X	X	
Clinical biochemistry ⁴	X	X	X	X	X	X	X	X	X	X	X	
Urinalysis and 24-hour urine protein quantification ⁵	X	X	X	X	X	X	X	X	X	X	X	
Fecal occult blood test	X	X	X	X	X	X	X	X	X	X	X	
12-lead ECG ⁶	X	X	X	X	X	X	X	X	X	X	X	
Echocardiography	X				X							
Thyroid function test	X				X		X		X	X	X	
Carcinoembryonic antigen (CEA)	X						X			X		
Pregnancy test (as required) ⁷	X				X		X		X	X		
Admission to and discharge from hospital		X										
Collecting AEs	X	X	X	X	X	X	X	X	X	X	X	X9
Information on subsequent treatment												X
Survival:											X	X

Notes:

- The baseline tumor assessment will be done within 2-3 weeks prior to administration, four sites (neck, chest, abdomen and pelvis) are evaluated in accordance with

RECIST1.1 criteria. Using the radiological (CT/MRI) examination, the baseline evaluation and post-treatment efficacy evaluation are performed with the same method and by the same investigator; tumor radiological assessment (CT or MRI) is performed every two cycles of treatment (8 weeks), until progression of disease. If the tumor is assessed as complete response or partial response (CR or PR), it needs to be re-confirmed 4 weeks later. If the subject receives the drug for less than 56 days, tumor assessment could be performed at the end of medication when necessary, according to investigator's judgement.

2. The vital signs include blood pressure, heart rate, respiratory frequency and temperature, and are monitored 2 hours(\pm 1 hour) after administration;
3. Hematological examination: red blood cell, hemoglobin, platelet count, neutrophil and its differential categories; prothrombin time (PT), activated partial thromboplastin time(APTT), thrombin time(TT), fibrinogen quantification(FIB) and INR. If the neutrophil is $\leq 1 \times 10^9/L$ or platelet count is $\leq 25 \times 10^9/L$, the frequency of repeated testing needs to be increased (once/2-3 days);
4. Serum chemistry: if 3 times elevation of ALT or AST occur during the trial, the frequency of repeated testing needs to be increased (2-3 times/week advised); the creatinine clearance at baseline is calculated based on the creatinine level (formula: $Ccr = (140 - \text{age}) \times \text{body weight}(\text{kg}) / [72 \times \text{Scr}(\text{mg/dl})]$ or $Ccr = [(140 - \text{age}) \times \text{body weight}(\text{kg})] / [0.818 \times \text{Scr}(\text{umol/L})]$, the unit of creatinine should be noted during the calculation of creatinine clearance, the result for female is the calculated result $\times 0.85$);
5. Routine urinalysis is used for measurement of urine protein, and needs to be repeated when urine protein ++ occurs once, 24-hour urine protein quantification is required for urine protein++ in consecutive two measurements;
6. 12-lead ECG is performed in screening period, 4 hours(\pm 1 hour) after administration on Day 7, 14, 21 and 28; and by the frequency of follow-up from the 2nd cycle of therapy;
7. Pregnancy test is performed in screening period, prior to administration, after administration for 28 days and after the end of each cycle of treatment;
8. The detailed administration method of Fruquintinib is provided in Section 5.1 in the protocol.
9. Adverse event is collected to 30 days after the last dose, and adverse event or abnormal laboratory findings that could not be recovered or explained need to be collected until they are recovered or explainable.

6.1 Screening examination and eligibility screening form

All the patients must be able to provide the written informed consent form prior to any specific study evaluation and procedure.

Investigators need to complete the eligibility screening form, where the information on screening of all the patients in accordance with the enrollment criteria and subsequent inclusion in or exclusion from the study are recorded.

6.2 Clinical Assessment

6.2.1 Effectiveness

6.2.1.1 Effectiveness endpoint

All the effectiveness endpoints in the randomized comparison study are secondary endpoints.

Secondary endpoints:

Objective response rate (ORR) determined in accordance with RECIST1.1

Disease control rate (CR+PR+SD), where SD \geq 8 weeks

Duration of response

Progression-free survival (PFS)

Overall survival (OS)

Primary effectiveness endpoint in the expansion part is the progression-free survival at Week 16

The secondary endpoints are DCR, ORR and OS

6.2.1.2 Assessment of effectiveness

The tumor is evaluated in accordance with RECIST1.1 criteria, and the detailed evaluation criteria are provided in Appendix 2. The radiological evaluation of tumors could use CT or MRI as decided by investigators, however, the apparatus and technical parameters should keep consistent throughout the study; contrast agent should be used in case of no contraindications. If the tumor evaluation has been performed 14-21 days before the first dose, and the same method and apparatus are used in the same hospital, this evaluation could be used as the baseline tumor evaluation. The baseline tumor evaluation should include neck, chest, abdomen, pelvis and any other sites that are suspected to have tumor lesions. Bone scan should be used for follow-up of the disease in patients with bone metastasis.

Record of target lesions: number, site and description of lesions, the maximum diameter measured for each lesion (except lymph node) and the minimum diameter measured for lymph node, sum of diameters including all the target lesions;

Subjects will receive the first tumor evaluation after 2 cycles of treatment, and one evaluation every two cycles subsequently, until progression of disease. If complete response or partial response occurs, it needs to be confirmed after 4 weeks. If the patient interrupts the dose for adverse drug reaction or other reasons, the tumor evaluation will be performed once every 8 weeks as originally scheduled. If the patient discontinues the study drug within 56 days, the tumor evaluation should be performed as early as possible after discontinuation of the drug.

6.2.2 Performance status

For ECOG PS score, evaluation of ECOG PS is advised to be performed by the same investigator throughout the study. See Appendix 1 for the details.

6.2.3 Clinical safety evaluation

6.2.3.1 Safety endpoints

The safety in both of the groups is comprehensively evaluated through the severity and incidence of adverse events, and graded in accordance with NCI CTCAE Version 4.0. Safety endpoints include:

Overall incidence of adverse events

Incidence of grade 3/4 adverse events, incidence of serious adverse events

Incidence of adverse events leading to permanent discontinuation and dose interruption/dose reduction

6.2.3.2 Evaluation of adverse events and safety laboratory parameters

Throughout the study, the clinical safety of the investigational therapy should be evaluated in accordance with NCI-CTC-AE V4.0.

Occurrence of adverse event must be evaluated at each clinical visit.

Complete history needs to be recorded at screening (including demographic profile; collection of history; symptoms recorded such as decreased appetite, asthenia, cough, dyspnea, hemoptysis, pain; record concurrent disease and concomitant medication, previous history of surgery; histologically or cytologically confirmed pathological diagnosis; as well as ECOG physical performance score)

Physical examination needs to be performed at baseline and each visit, or more frequently according to clinical indications.

12-lead ECG is performed at baseline, and whenever clinically indicated in the study.

The clinical serum chemistry, blood and urine tests are performed at baseline, after treatment and during follow-up period according to the study plan.

The detailed evaluation items include:

- ✓ Hematological examination: red blood cell, hemoglobin, platelet count, neutrophil and differential leukocyte count; thrombin time(TT), prothrombin time(PT), activated partial thromboplastin time(APTT), fibrinogen(FIB) and INR.
- ✓ Routine urinalysis: pH, specific gravity, protein, cast, red blood cell, glucose and urine acetone bodies
- ✓ Fecal occult blood test
- ✓ Clinical biochemistry: total protein (TP), albumin (ALB), globulin (G), A/G, glucose, urea nitrogen, creatinine, alkaline phosphatase (ALP), lactate dehydrogenase (LDH), total bilirubin, glutamic-oxaloacetic transaminase (AST), glutamic-pyruvic transaminase (ALT), calcium, phosphorous, magnesium, potassium, sodium, chlorine, amylase, uric acid
- ✓ Routine thyroid function test: at least free triiodothyronine(FT3), free thyroxine(FT4) and TSH
- ✓ 12-lead ECG: P-R interval, QRS interval, Q-T interval, QTc and diagnosis
- ✓ Echocardiography: in particular pay attention to left ventricular ejection function
- ✓ Tumor markers: carcinoembryonic antigen(CEA)

6.2.4 Measurement of drug concentration and pharmacokinetic study

Determination of the drug and its metabolites (metabolite HM5013199 and HM5012569) in the blood sample is performed by Covance pharmaceutical R&D (Shanghai) Co., Ltd., the specific determination method for the plasma drug concentration is established by the testing unit under the assistance from Hutchison Medi Pharma (Shanghai) Co., Ltd., the method and course of experiment are described in detail in the clinical study report. The Drug Metabolism and Kinetics from Hutchison Medi Pharma (Shanghai) Co., Ltd. is responsible for the calculation and analysis of the PK parameters.

Evaluation of the pharmacokinetic profile is performed for all the subjects in the randomized study, the blood collection schedule for the pharmacokinetic (PK) study during the administration is provided in Table 8 and 9.

2.5ml blood is collected each time, a total of about 50ml blood is estimated to be required for PL evaluation.

The sampling time and actual time should be well recorded on the PK sampling page of eCRF/CRF. Any important information related with sampling or blood collection (eg., loss of blood sample, delayed sampling, hemolysis) should also be recorded in the column of note.

The guidelines on PK sample processing and transportation are provided in Appendix 5.

The basic schedule for blood sampling in Group A (4mg qd daily) is provided in Table 8. If there is no change in the dose in the full-range of PK study (in the first 3 cycles of therapy), only the blood samples on D1/2 and D21/22 need to be collected for PK analysis. If the dose

is changed (dose interruption or dose reduction), the PK sampling should comply with the principle of ensuring collection of the new steady state after dose change and resumption of administration. Details are listed below:

- 1) All the PK sampling days must be the follow-up days scheduled in the protocol.
- 2) If the subject interrupts or reduces the dose for adverse reaction 22 days after administration, the subject is hospitalized on the first follow-up day (eg., one of Day 42, 56, 70 or 84) after administration for ≥ 14 days (reaching the steady state) after dose reduction, and the blood samples at 0, 1, 2, 4, 8 and 24 hours after administration on that day (until before administration on the following day) are collected.
- 3) If the dose is changed prior to Day 21, the originally scheduled plan for blood collection on Day 21 is given up. The remaining blood collection plan refers to the above Item 2), i.e., the subject is hospitalized on the first follow-up day (eg., one of Day 28, 42, 56, 70 or 84) after administration for ≥ 14 days (reaching the steady state) after resumption of the administration, and the blood samples at 0, 1, 2, 4, 8 and 24 hours after administration on that day (until before administration on the following day) are collected. Blood samples from only 3 intensive time periods are collected at most for each patient.

Table 8. Blood collection schedule in Group A (4mg qd daily):

Pharmacokinetic Sampling Times						
Time	10 minutes before administration	Administration (in the morning)	1 h	2 h	4 h	8 h
Day 1	√		√	√	√	√
Day 2	√					
D21#	√		√	√	√	√
D21#	√					
After the dose is adjusted to 3mg or 2mg, the blood samples at 0,1,2,4,8 and 24 hours on the first follow-up day (any one of D28,D42,D56,D70 or D84) are collected after consecutive administration for 14 days (reaching the steady state)						
D28/D42/D56/D70/D84*	√		√	√	√	√
D29/D43/D57/D71/D85*	√					

Note: √ represents need of blood collection;

* represents blood collection on that day only when required. Only one of the 5 time periods, i.e., D28/29, D42/43, D56/57, D70/71 and D84/85 is selected for blood collection;

represents if the dose is changed 21 days ago, the plan for blood collection on D21/22 is given up. The subsequent blood collection day is one day marked *, the principle on decision is provided in the detailed rules above.

The basic schedule for blood collection in group B (5mg qd 3-weeks on/1-week off) is provided in Table 9. If there is no change in the dose in the full-range of PK study (in the

first 3 cycles of therapy), only the blood samples on D1/2 and D21/22 need to be collected for PK analysis. If the dose is changed (dose reduction), the PK sampling should comply with the principle of ensuring collection of the new steady state after dose change and resumption of administration. Details are listed below:

- 1) If the dose is changed, the administration period needs to be re-calculated; according to the clinical study protocol, the patient needs to return to the hospital for follow-up on Day 14 in the new administration period.
- 2) If the subject reduces the dose for adverse reaction 22 days or more after administration, the subject is hospitalized on Day 14 after consecutive administration (reaching the steady state) after dose reduction, and the blood samples at 0, 1, 2, 4, 8 and 24h after administration on that day (before administration on the following day) are collected.
- 3) If the dose is changed prior to Day 21, the originally scheduled plan for blood collection on Day 21 is given up. The remaining blood collection plan refers to the above Item 2), i.e., the subject is hospitalized on follow-up on Day 14 after resumption of the administration, and the blood samples at 0, 1, 2, 4, 8 and 24 hours after administration on that day (until before administration on the following day) are collected. Blood samples from only 3 intensive time periods are collected at most for each patient.

Table 9. Blood collection schedule in group B (5mg qd 3-week on/1-week off):

Pharmacokinetic Sampling Time						
Time	10 minutes before administration	administration (in the morning)	1 h	2 h	4 h	8 h
Day 1	√		√	√	√	√
Day 2	√					
D21#	√		√	√	√	√
D21#	√					
After the dose is adjusted to 4mg 3-week on/1-week off or 3mg 3-week on/1-week off, the blood samples at 0, 1, 2, 4, 8 and 24 hours on Day 14 of consecutive administration after dose reduction are collected.						
Day 14 of consecutive administration after dose reduction*	√		√	√	√	√
Day 15 of consecutive administration after dose reduction *	√					

Note: √ represents need of blood collection;

* represents blood collection on that day only when required.

represents if the dose is changed 21 days ago, the plan for blood collection on D21/22 is given up. The subsequent blood collection day is one day marked *, the principle on decision is provided in the detailed rules above.

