1.2.2.5 Pharmacodynamics results

Preliminary results from the phase I pharmacokinetic clinical study of Fruquintinib in treatment of advanced solid tumors:

The very low clearance rate and low tissue distribution of Fruquintinib in humans allowed a high plasma exposure after oral administration even at a low dose, and Fruquintinib had a long elimination phase half-life (about 42 hours). Fruquintinib was well and rapidly absorbed after oral administration of one single dose of 1mg to 6mg, which was in line with the linear pharmacokinetic profile, and its exposure was linearly increased with the increase of dose. A steady state was considered after consecutive administration of Fruquintinib for 14 days; the exposure at the steady state was linearly increased with the increase of dose over the range of 1mg - 6mg; the long half-life of Fruquintinib supported the administration method of once daily, and this method could make the plasma drug concentration at steady state fluctuate within a very small range but produce about 3~4 of accumulation at steady state, which was resulted from the linear superposition of the effect after multiple doses. This method was still in accordance with the linear pharmacokinetic profile after multiple doses.

Study on the effect of food on the pharmacokinetics of Fruquintinib (preliminary results):

It was preliminarily found in one monocentric, randomized, open-label, single-dose, two-period, cross-over clinical study on the effect of food on the pharmacokinetics of Fruquintinib capsule in healthy volunteers that food had no statistically significant effect on the exposure (AUC) and peak concentration (C_{max}) of 4mg Fruquintinib capsule after single dose in healthy males, however, the time to reach the peak (T_{max}) was delayed by food.

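### Section 6.2.4 triggers repeat PK sampling on different dose changes in the two arms, so some Group B Day 21 profiles may be taken below steady state

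*Protocol*

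**What the plan says.** Section 6.2.4 asks for intensive profiles on Day 1/2 and Day 21/22 when the dose stays the same over the first three cycles, and gives each arm its own rules when it does not.

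- **Group A.** The lead text applies when the dose "is changed (dose interruption or dose reduction), the PK sampling should comply with the principle of ensuring collection of the new steady state". Rule 2 begins "If the subject interrupts or reduces the dose for adverse reaction 22 days after administration", but then counts the 14 days from a reduction. The Table 8 row heading for the replacement profile names only the reduced doses, 3 mg and 2 mg.
- **Group B.** The lead text says "If the dose is changed (dose reduction), the PK sampling should comply with the principle of ensuring collection of the new steady state". Rule 2 begins "If the subject reduces the dose for adverse reaction 22 days or more after administration". The replacement rows of Table 9 apply only after a reduction.
- **Rule 3.** The trigger sentence is the same in both arms: "If the dose is changed prior to Day 21, the originally scheduled plan for blood collection on Day 21 is given up". For Group B the replacement is then set so that "the subject is hospitalized on follow-up on Day 14 after resumption of the administration".

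Section 1.2.2.5 gives the basis for the 14 days: "A steady state was considered after consecutive administration of Fruquintinib for 14 days", with a half-life of about 42 h and accumulation of about 3 to 4.

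Section 5.9.1, and section 5.9.2 on hand-foot syndrome and stomatitis, leave open a restart without reduction. Table 7 in section 5.9.3 has dosing restart at the reduced dose.

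The Synopsis lists comparing the PK of the two regimens as a secondary objective (section 2.2 words it as exploring) and plans to relate PK to the main safety parameters. Section 8.2.2 analyses Cmax and AUC with dose group as the fixed factor.

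**The concern.** Two patients with the same history can be sampled differently because of their arm. Each pauses before Day 21 and restarts the unchanged dose. In Group A this counts as a changed dose, so the Day 21/22 profile is dropped and replaced after at least 14 days of dosing. In Group B, read literally, nothing has changed: Day 21/22 stands and no later profile is drawn.

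If the restart came shortly before Day 21, the Group B profile is below steady state by the protocol's own criterion. The error runs one way, towards understating Group B exposure. It also falls on patients who typically paused for toxicity, so low measured exposure would be paired with toxicity in one arm only. A later analysis can exclude such a profile but cannot recover a steady-state sample that was never drawn.

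**Working it through.** **Inputs.** From section 1.2.2.5: half-life about 42 h, steady state after 14 consecutive days, accumulation about 3 to 4. From section 8.3: 20 patients in Group B. Dosing is once daily. The number of patients who paused before Day 21 is not given.

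**Reproducing the plan's figures.** In a one-compartment linear model, the fraction carried from one day to the next is q = 2^(−24/42) = 0.673.

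- Accumulation = 1/(1 − q) = 3.06, against the stated 3 to 4.
- Fraction of steady state after 14 doses = 1 − q^14 = 99.6%.

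Both agree with the protocol, so the 14-day rule is sound.

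**Day 21 exposure after a pause.** Let the patient miss L days and then take r daily doses up to and including Day 21, at the same dose. Relative to no pause:

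ratio = (1 − q^r + q^(r+L) − q^21) / (1 − q^21)

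For r = 3, L = 7: (1 − 0.3048 + 0.0190 − 0.0002) / 0.9998 = 0.714.

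| Doses since restart | 2-day pause | 7-day pause | 14-day pause |
|---|---|---|---|
| 1 | 63% | 37% | 33% |
| 3 | 83% | 71% | 70% |
| 5 | 92% | 87% | 86% |
| 6 | 95% | 91% | 91% |
| 7 | 97% | 94% | – |
| 10 | 99% | 98% | – |

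The shortfall passes about 10% only with about five or fewer doses since restart, and is 2% or less from ten doses on.

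**Sensitivity.** The 71% becomes 76% for a 36 h half-life and 68% for 48 h. At the upper stated accumulation of 4, q = 0.75, which implies a half-life of about 58 h. Ignoring carry-over from before the pause, 1 − 0.75^r gives 76% at five doses, 87% at seven and 94% at ten, so the window is somewhat longer.

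**Effect on the group mean (assumed frequencies).** Fall in the mean = (affected/20) × shortfall.

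- 1 of 20 at 20%: 0.05 × 0.20 = 1%.
- 4 of 20 at 30%: 0.20 × 0.30 = 6%.
- 4 of 20 at 50%: 0.20 × 0.50 = 10%, an unfavourable case.

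For scale, the nominal daily dose ratio is 5/4 = 1.25.

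**The case against.** The strongest reply is that this is loose drafting in both arms, not a clean rule in A and none in B. Rule 3 alone cancels Day 21, and its trigger sentence is identical in the two arms. Its Group B continuation counts from resumption, which presupposes a pause, so a site could fairly apply it to interruptions. Group A slips to reduction in rule 2 and in Table 8. This stands, and it is why the point is one of reconciling the text. It does not remove the problem: the Group B lead sentence still defines a change as a reduction, and Table 9 has no row for a patient who restarts the same dose.

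A reader might infer that every Group B patient who resumes after a pause is profiled below steady state. The documents do not support that. The pause must come before Day 21, the dose must be unchanged, and the restart must be only days before Day 21. On the Table 7 path a pause ends in a reduction, which does trigger re-sampling.

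A reader might also infer near-washed-out profiles: off drug on Days 14–21, the model gives about 4%. But Table 9 samples around an administration, and such a patient has none on Day 21.

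Nor do the documents show that the PK comparison is biased. The number affected is unknown, section 8.2.2 ties its parameters to no sampling day, and an analysis plan not shown may exclude such profiles. Section 5.7 has dosing times and missed doses recorded, so affected profiles can be found. Finally, the choice of regimen rests on safety, tolerability and efficacy (sections 3.1.2 and 8.2.4), not on this comparison.

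**Conclusion.** The point holds as an inconsistency with a limited, one-directional consequence. The event that triggers re-sampling differs between the arms and is not stable within either. Under the literal Group B text, a same-dose restart with about five or fewer doses before Day 21 leaves a profile more than about 10% below steady state; the Group A text calls for a replacement in the same situation.

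The effect on the Group B mean is probably a few percent: 1–6% if 1 to 4 of 20 patients have a 20–30% shortfall. Those frequencies are assumptions. Section 3.1.2 reports grade 3 or higher events in 8 of 20 Group B patients but does not say how many paused before Day 21. The individual figures rest on one-compartment linear kinetics with the stated half-life. The exposure–safety analysis is more exposed than the mean, because the affected patients are likely to be those with toxicity.

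This is worth correcting because it costs little and removes a difference in sampling that depends on arm. It does not undermine the trial's main conclusions.

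**What to change.** **In section 6.2.4:**

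- Use one pre-Day-21 trigger in both arms: an unplanned interruption (not the scheduled off week) or a reduction before Day 21 cancels the Day 21/22 profile and moves it to after 14 consecutive dosing days following resumption.
- Align the lead sentences, rule 3 and the row headings of Tables 8 and 9 with that trigger. Make the trigger and the 14-day count in Group A rule 2 name the same event.
- Leave Group B rule 2 (Day 22 onward) limited to reductions. Extending it to same-dose interruptions would add an intensive period and a hospital stay, and cannot affect a Day 21 profile already taken.
- Group B rule 1 recalculates the administration period when the dose is changed. State whether that follows from the wider sampling trigger, so that a PK definition does not alter dosing by accident. The differing restart wording in sections 5.9.1, 5.9.2 and Table 7 also needs reconciling; which wording is right is not a statistical question.

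**For profiles already collected,** exclude from the between-group steady-state comparison, in both arms, any Day 21 profile not preceded by 14 consecutive days at the same dose. Section 3.1.2 reports all 40 randomised patients enrolled by the September 2013 cut-off, so this is probably the more useful half of the fix.

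**Cost.** A few words of text and one analysis rule. Before Day 21 the profile is moved, not added, and the cap of three intensive periods still holds. A few Group B profiles come later, and a few may be lost from the comparison.
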